Stage/Aim 1: Refine the *Mobile Anger Reduction Intervention (MARI)* app in two successive cohorts of n=5 Veterans with PTSD and problematic anger. After the first cohort uses the application for a period of four weeks, a qualitative and quantitative evaluation will be conducted and each participant will be interviewed. Revisions will then be made based on these evaluations before another cohort of n=5 Veterans is treated. Again, following treatment an evaluation will be completed and further revisions will be made to the treatment. The resulting iteration of the treatment will be used in the subsequent pilot randomized controlled trial (Aim 2).

Stage/Aim 2: a) Evaluate the feasibility of recruitment, randomization, and retention procedures in a pilot study comparing MARI to a contact control condition (mindfulness app); and b) utilize psychophysiological and electronic diary monitoring to determine whether this assessment could be used as an outcome or mechanistic variable in a subsequent randomized clinical trial application focused on evaluating the efficacy of the MARI intervention. Aims 2a and 2b will be evaluated in a third cohort of 40 individuals with PTSD and self-reported problematic anger that will be randomized in a 1:1 ratio to MARI (n = 20) versus the mindfulness control condition (n = 20).

Design

The proposed research project is comprised of two stages. Each stage has its own aim. In the first stage (Stage/Aim 1) a successive cohort design (Epstein et al., 2007) will be used to refine the MIRA intervention two cohorts of 5 participants with PTSD and problematic anger. In the next stage (Stage/Aim 2), we will conduct a small, randomized controlled trial of MIRA compared to a mindfulness intervention (matched for time and participant contact) in a third cohort of 40 individuals.

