Stage/Aim2: We propose to recruit 40 participants for the second stage of the study. Recruitment procedures and inclusion/exclusion criteria will be the same as those from Stage/Aim 1. After an initial phone screen, interested participants will come in for a pretreatment assessment. After confirming that they meet study criteria (including completion of a diagnostic interview to confirm PTSD diagnosis), they will complete baseline assessments (see assessment table above). If participants are eligible, they will sign a Duke informed consent form for the mobile health procedures of the study, which include wearing a portable heart rate monitor and using a smart phone for recording information about affect for 72 hours. After this baseline period, they will return the Duke equipment. They will then be randomized to either the MARI or mindfulness control condition (n = 20 per condition). Participants will be shown how to access their assigned intervention via Duke-owned smartphone. At the end of the first

Research Protocol, Version Date: 7/28/2022

week of treatment, participants will be contacted over the phone to check in about whether they have encountered any problems with the app, answer any questions that they have, and remind them to use the app. They will also complete a short interview about their impressions of the app at that point (see One Week Interview). They will be asked to continue to use the mobile application in the Duke study for the next four weeks. Next, they will do the ambulatory HRV monitor and electronic diary for a period

of 72 hours. Then, participants will return for an in-person, post-treatment visit. Finally, they will complete a three-month follow-up visit (see Figure 10 below).

Mobile Device Use

Study participants will access the MARI and mindfulness apps using Duke-owned mobile devices and a separate Duke IRB protocol is in place for this part of the study. These data collected with Duke-owned devices will be Duke-owned data, not VA-owned. This Duke-owned data will then be combined with VA data, and transferred via a VA-owned FIPS-encrypted thumbdrive or via VA's S.A.F.E.

Risk/Benefit Assessment

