We will also conduct a qualitative analysis of the weekly anger and hostile interpretation bias data by graphing these measures across time for each participant to determine if and when these measures decrease, as this will help us to determine whether there is an optimal dose of treatment and number of treatment sessions across participants.

In order to analyze descriptive data from the qualitative interviews, we will need access to NVivo 11 software, which is not available through VINCI. Therefore, deidentified data (with none of the 18 HIPAA identifiers or the study ID) will be moved to Duke University Medical Center for analysis. Only fully deidentified data will be stored on Duke computers. Any data movement to Duke will be accomplished using email. Any data transfer from Duke machine(s) back to VA will also be done via email. Data will be stored at Duke on a protected server to which only [name] and her study staff have access; data are encrypted at rest.

Research Protocol, Version Date: 7/28/2022

Page 14 of 23

Stage/Aim2: Recognizing that it is inappropriate to examine efficacy in a small pilot trial, we will focus on feasibility and acceptability objectives (Leon et al., 2011). As appropriate for this stage of treatment development and evaluation, analysis and interpretation will focus on describing the primary outcomes: acceptability of the intervention and feasibility of the trial approach. We will examine the recruitment rate, treatment retention, patient satisfaction, and app utilization as primary outcomes.

We will also describe Nightly Diary outcomes, including: daily emotions and pain reported; how helpful the app was; whether it made them feel differently about things that happened during their day. Additionally, although we will not be able to statistically analyze group differences, we will describe group differences in clinical (anger-related) outcomes and functional outcomes, including whether changes were observed in the expected directions (reductions in anger variables and increases in functional outcomes).

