Finally, mixed between-within repeated measures ANOVA will be used to examine potential treatment effects on overall HRV. Specifically, 2 (Treatment) X 2 (Time) ANOVAs will be used to model SDNN, LF, and HF to determine whether overall HRV increases from pre- to post-treatment as a result of IBM relative to the control condition. We will also examine changes from pre- to post-treatment in physiological reactivity to anger. Using methodology that we have applied to examine mood-related autonomic arousal (e.g., Dennis et al., 2017), we will use multilevel modeling (MLM) to examine short-term changes in HRV and HR associated with momentary assessments of anger. MLM is appropriate for analyzing unbalanced repeated-measures data and can incorporate both person-level predictors (e.g., treatment condition) and episodic predictors (e.g., anger; . We will thus examine whether the association between anger and autonomic arousal (i.e., HR, SDNN, LF, and HF) attenuates following treatment, particularly for participants assigned to the MIRA condition. We will also examine whether this expected decrease in autonomic reactivity is associated with improved functional outcomes and decreased anger outcomes.

Privacy, Confidentiality, and Information Security

1. Lists of Data Reviewed and/or Collected for Screening/Recruitment and Conduction of Study:

The Personal Health Information that will be obtained, used, and/or shared for this study includes:

Identifier(s)	Source(s) of Health Information
Names	Medical history & physical exam
	information
All geographic subdivisions smaller than	igert Photographs, videotapes, audiotapes,
a State, including street address, city,	or digital or other images
county, precinct, and zip code. Describe:	
Participants' addresses will be collected	
during the study in order to pay them for	
participation.	

Identifier(s)	Source(s) of Health Information
All elements of dates (except year) for	Biologic specimens (e.g., blood,
dates directly related to an individual,	tissue, urine, saliva). Describe:
including birth date, admission date,	, , , , , , , , , , , , , , , , , , , ,
discharge date, visit or treatment dates, etc.;	
and all ages over 89, Describe: Date of	
participation will be collected. In addition,	
treatment records, laboratory results, etc.	
will be collected.	
Telephone numbers	
Fax numbers	Diagnostic / Laboratory test results
Electronic mail addresses	Operative reports
Social Security Numbers	Imaging (x-ray, CT, MRI, etc.)

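### HRV analysis: the 2 x 2 ANOVA is valid, but it fixes the slope on the pre-randomisation recording at 1; estimating that slope would usually sharpen the arm difference if pre and post SDs are similar

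*Combined protocol and SAP*

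**What the plan says.** The HRV analysis is in Data Analysis and Statistical Considerations, Stage/Aim2. It states that "mixed between-within repeated measures ANOVA will be used to examine potential treatment effects on overall HRV" and specifies that "2 (Treatment) X 2 (Time) ANOVAs will be used to model SDNN, LF, and HF", with the purpose "to determine whether overall HRV increases from pre- to post-treatment as a result of IBM relative to the control condition". The pre-treatment value enters only as a level of Time, and no covariate is named. The multilevel model later in the same paragraph can take person-level predictors. It concerns momentary reactivity to anger rather than overall HRV, however, and does not list baseline HRV.

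The Design section (Stage/Aim2) puts the 72-hour baseline monitoring before allocation: "After this baseline period, they will return the Duke equipment. They will then be randomized". A second 72-hour recording follows treatment.

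Two passages set the weight of this analysis. Aim 2b wants the monitoring "to determine whether this assessment could be used as an outcome or mechanistic variable in a subsequent randomized clinical trial application". The Stage/Aim2 analysis text opens by accepting that "it is inappropriate to examine efficacy in a small pilot trial" and names recruitment rate, retention, satisfaction and app use as the primary outcomes. HRV is not among them.

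**The concern.** With two time points, the interaction test in a 2 x 2 mixed ANOVA compares the arms on post minus pre. This subtracts the whole of each person's baseline value. Unless the regression slope of post on pre is 1, some other multiple of the baseline removes more noise. With equal SDs the slope equals the correlation, so it is below 1 whenever the correlation is below 1.

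The baseline recording precedes randomisation, so it is a legitimate covariate, and its slope can be estimated without changing the question. Under randomisation the arms have the same expected baseline. The change-score contrast and the baseline-adjusted contrast therefore estimate the same expected arm difference.

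Only precision is at stake. The arm difference and its interval are one input to the Aim 2b judgement on whether HRV could serve as an outcome in a later trial.

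**Working it through.** The plan gives no power, effect size or precision figure for HRV, so there is none to reproduce.

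**Inputs from the documents.** Stage 2 size: "We propose to recruit 40 participants for the second stage of the study", allocated 1:1, so n = 20 per arm and N = 40. There is one pre-randomisation and one post-treatment recording.

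**Assumed inputs (not in the documents).** Pre-post correlation rho; SD ratio k = SD post / SD pre; complete pairs, with 32 completers as an alternative; a linear slope common to both arms; a normally distributed baseline.

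**Formulas, with the pre SD set to 1.**
- Change score (the ANOVA interaction): variance = (2/n)(1 + k² − 2k·rho).
- Baseline-adjusted: average variance over randomisations = (2/n)·k²(1 − rho²)·(N − 3)/(N − 4). The last factor is the average price of estimating one slope. At N = 40 it is 37/36 = 1.028.
- Ratio, adjusted / change = k²(1 − rho²)/(1 + k² − 2k·rho) × 37/36. At k = 1 this is (1 + rho)/2 × 37/36.

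**Equal SDs, N = 40.** For example, at rho = 0.7 the change-score variance is 0.1 × 0.6 = 0.0600 and the adjusted variance is 0.1 × 0.51 × 37/36 = 0.0524, a ratio of 0.874.

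| rho | variance ratio | variance reduction | 95% CI narrower by |
|---|---|---|---|
| 0.5 | 0.771 | 22.9% | about 12% |
| 0.7 | 0.874 | 12.6% | about 6% |
| 0.8 | 0.925 | 7.5% | about 4% |
| 0.9 | 0.976 | 2.4% | about 1% |

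Break-even is at rho = 72/37 − 1 = 0.946, or 0.931 with 32 completers.

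**Unequal SDs, N = 40.**

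| k | ratio at rho 0.5, 0.7, 0.8, 0.9 | change score better when |
|---|---|---|
| 0.8 | 0.59, 0.65, 0.66, 0.63 | never |
| 1.1 | 0.84, 0.95, 0.99, 1.03 | rho 0.81 to 0.96 |
| 1.25 | 0.92, 1.01, 1.03, 0.98 | rho 0.68 to 0.88 |

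**Largest average loss.** The first factor of the ratio cannot exceed 1, because the residual variance from the best linear prediction cannot exceed the variance of the change. It equals 1 when rho = 1/k. The average loss is therefore at most 37/36 − 1 = 2.8% in variance. With the lost degree of freedom, that is 1.5% in CI width. With 32 completers the figures are 29/28 − 1 = 3.6% and 1.9%.

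**Loss in a single trial.** For a normal baseline, the slope-estimation term in one realised trial is distributed as F(1,38)/38. Its median is 1.2% and its 95th percentile 10.8%, and it exceeds 2.8% with probability about 31%. With 32 completers the 95th percentile is 13.9%.

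**Simulation check (40,000 trials per setting, 20 per arm, k = 1).** Ratios were 0.766, 0.870, 0.923 and 0.980 at rho 0.5, 0.7, 0.8 and 0.9 with a normal baseline, and 0.774, 0.866, 0.927 and 0.976 with a lognormal one. Type I error at nominal 0.05 was 0.047 to 0.051 for the interaction test and 0.047 to 0.052 for the adjusted test. At rho = 0.7 the mean CI width was 0.99 SD for the change score and 0.92 SD adjusted.

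**The case against.** The strongest case against raising this is that nothing in the plan is wrong. The interaction test is valid, already uses the baseline recording, and answers the stated question, so choosing between two unbiased estimators for a non-primary index could be called preference. The consequence is small: no decision in the documents turns on an interval of 0.92 rather than 0.99 SD. Compliance, completeness, SDs and the pre-post correlation bear more directly on Aim 2b than a slightly sharper contrast. The sign of the benefit also depends on quantities that the documents do not give.

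Most of this stands, and it sets the weight of the point. The stakes are low, and the gain can be called usual only on the assumption of similar pre and post SDs.

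It does not remove the point. The covariate is already collected, the target is unchanged, and the pre-to-post description can be kept in full. With the correlation and SD ratio unknown beforehand, estimating the slope risks a small average loss for what may be a material gain, while fixing it at 1 relies on a value that nothing in the documents supports.

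**Conclusion.** The point holds as an optional precision improvement. Assuming equal SDs and 40 complete pairs, adjustment cuts the variance of the arm difference by about 23% at rho 0.5, falling to about 2% at rho 0.9. Under a linear common slope and a normal baseline, it costs at most 2.8% on average over randomisations (3.6% with an assumed 32 completers).

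Three stronger readings are tempting, and none is supported.
- A reader might infer that the ANOVA is invalid or ignores baseline HRV. It does neither: its interaction term holds its error rate and uses the baseline with slope 1. This applies to the interaction, which the stated purpose implies but the text does not name. The Treatment main effect would average in the pre-randomisation value.
- A reader might infer that adjustment always gains. It does not when the post SD exceeds the pre SD over some range of correlations.
- A reader might take 2.8% as a ceiling for this trial. It is an average; with chance baseline imbalance the slope-estimation cost can be larger (95th percentile about 11%).

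Nor does this touch the trial's conclusions on feasibility and acceptability, which do not rest on HRV.

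**What to change.** In the Stage/Aim2 analysis text, replace the ANOVA sentences with wording such as: *For each of SDNN, LF and HF, the treatment effect will be estimated as the arm difference in the post-treatment value from a regression on arm and the pre-randomisation value, with its 95% CI. Pre and post means and SDs, mean change by arm, and the pre-post correlation will be reported as description for Aim 2b.*

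If the change scale is preferred, regress change on arm and the pre-randomisation value. The arm difference and CI are identical, because only the baseline coefficient shifts, by 1. If the 2 x 2 ANOVA is still shown, label it as supporting, so that each index has one treatment-effect estimate.

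The change costs two sentences, one degree of freedom and no new data, besides the possible small loss of precision quantified above. The reported SDs and correlation would also show which estimator suits the later trial.
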